### Hypotheses

The research question will be addressed in this study by testing the following hypotheses:

1. An automated recommendation on PONV prophylaxis that is based on a patient-specific PONV risk that is sent by email to individual anesthesia providers the day before the scheduled procedure increases the adherence to PONV guidelines.

2. An automated recommendation on PONV prophylaxis that is based on a patient-specific PONV risk that is presented at the start of anesthesia increases the adherence to PONV guidelines (and has an added value to the automated email recommendation).

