## Study Design and Participants

### Study design

The time series consists of three phases. The first phase is the preintervention phase – i.e. before the decision support has been implemented. The second phase is the first intervention phase in which the email with recommendations is being sent (Figure 1). The third phase is the second intervention phase in which the real time decision support guidance (Figure 2) is being displayed along with the email intervention.

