### Study population

All adult patients (18 years and older) that are scheduled for an elective surgical procedure under general anesthesia within the study period will be considered eligible. We will exclude patients undergoing emergency surgery, and patients who will not go to the PACU to recover (i.e. patients that are transferred directly to the Intensive Care Unit or die intraoperatively). Procedures that only require a sedative level of anesthesia will be excluded from the analysis.

[figure not shown]

Figure 1. Screenshot example of email recommendations.

[figure not shown]

Figure 2. A screenshot mockup of the real-time decision support within our perioperative information management system.

Table 1 - Apfel's simplified risk score

Factor	Risk Score
Gender – Female	1
History of PONV/Motion sickness	1
Expected postoperative use of opioids	1
Non-smoker	1

Table 2 - Relation between predicted risks and recommendations

Number of PONV risk factors	Predicted PONV risk	Recommended number of interventions
0	0%	0
1	20%	1
2	40%	2
3	60%	3
4	80%	4

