## Outcome

### Primary outcome

The adherence to PONV guidelines will be used as the primary outcome. This is defined as an exact match between the recommended and applied numbers of interventions. Either a lower or a higher number of interventions will be considered as noncompliant to the guidelines. For the primary analysis the overall change in adherence as well as the added values of the different decision support elements to that adherence will be quantified. Medications with antiemetic properties will be considered prophylactic administrations, if they occur before the documented anesthesia stop time. We will consider scopolamine, dexamethasone, ondansetron, haloperidol, droperidol as prophylactic medications.

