### Data collection

We plan to use the Perioperative Data Warehouse (PDW), an IRB-approved data repository, as the data source to study the effects of the decision support on the application of prophylactic interventions for PONV and the occurrence of PONV within the PACU.

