### Statistical analysis plan

A two-sided alpha of 0.05 will be considered to be statistically significant. Continuous variables will be visually assessed for a normal distribution using histograms and QQ-plots. In descriptive statistics, parametric variables will be expressed as means with standard deviations, nonparametric variables will be expressed as medians with interquartile ranges, and discrete variables will be expressed as numbers with percentages. The primary analysis will be performed under the intention-to-treat principle. We will compare the incidence of the primary and secondary outcomes between the study groups utilizing analysis of variances to compare the means of multiple groups.

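### Three sequential phases are compared only by an ANOVA of means, with no calendar-time term and no contrast for the effects sought, so any secular drift would be folded into the phase differences

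*Combined protocol and SAP*

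**What the plan says.** The Study design section states: "The time series consists of three phases". The first precedes decision support, the second has the email alone, and in the third "the real time decision support guidance (Figure 2) is being displayed along with the email intervention". No concurrent or randomized comparison group is described.

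The first entry under Hypotheses concerns a recommendation "sent by email to individual anesthesia providers the day before the scheduled procedure". The second concerns a recommendation at the start of anesthesia that also "has an added value to the automated email recommendation". Under Primary outcome, where adherence is an exact match for each patient, the plan promises that "the overall change in adherence as well as the added values of the different decision support elements to that adherence will be quantified". The target quantities are therefore named.

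The Statistical analysis plan sets a two-sided alpha of 0.05 and the intention-to-treat principle. Its one between-group method compares outcomes "between the study groups utilizing analysis of variances to compare the means of multiple groups". It does not define the groups; the phases are the only candidates. It gives no time term, contrast, covariate, multiplicity rule or allowance for correlated cases. Patients are eligible if they are "scheduled for an elective surgical procedure under general anesthesia within the study period will be considered eligible", but the text available for this review gives no switch dates or phase lengths.

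**The concern.** There are two separate gaps.

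First, the analysis does not deliver the quantities that the protocol promises. A three-group F test asks whether the means differ at all. It does not isolate the email effect or the added effect of the guidance, and it gives neither a direction nor an interval.

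Second, phase and calendar time change together. If adherence moves for another reason (staffing, case mix, supply, other initiatives), a comparison of phase means cannot separate that movement from the decision support. More patients make the mixed answer more precise, not less biased. The intention-to-treat principle does not help, because no allocation is randomized.

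Both hypotheses and the primary outcome depend on this one sentence of the plan.

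**Working it through.** The documents give no baseline adherence, drift, volume, phase length or power calculation, so there is no stated figure to reproduce. Everything below except alpha rests on assumptions: 40% adherence in phase 1, equal 6-month phases, linear drift, independent cases.

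**1. Bias.** Under linear drift each adjacent phase difference contains slope × phase length, and phase 3 minus phase 1 contains twice that. At 0.25 pp/month: 0.25 × 6 = 1.5 pp per step and 3.0 pp overall.

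**2. ANOVA rejection with no true effect.** Use the noncentral F with λ = n Σ(p − p̄)²/σ². At 0.25 pp/month the phase means are 40, 41.5 and 43%, so Σ(p − p̄)² = 2 × 0.015² = 0.00045, and the mean of p(1 − p) is 0.2426. With n = 3,000, λ = 3,000 × 0.00045/0.2426 = 5.56, which gives 55% rejection.

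| Drift (pp/month) | Spurious step (pp) | n = 1,000 | n = 3,000 | n = 8,000 |
|---|---|---|---|---|
| 0.1 | 0.6 | 7% | 12% | 26% |
| 0.25 | 1.5 | 21% | 55% | 94% |
| 0.5 | 3.0 | 68% | 99% | 100% |

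**3. Masking.** Take a true 3 pp gain with drift of −0.25 pp/month. The observed step is 3 − 1.5 = 1.5 pp. Power for that step (two-proportion z test) falls from 27 / 66 / 97% to 10 / 22 / 49% at 1,000 / 3,000 / 8,000 per phase.

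**4. Correlated cases.** With no drift, a shared weekly shift of SD 2 pp gives a phase mean the variance 0.24/n + 0.02²/26. The ANOVA then rejects in about 6 / 8 / 14% instead of 5%.

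**5. Does a time term help?** In 1,000 simulations per setting (40% baseline, 1,000 or 3,000 per phase, no effect, drift of 0 to 5 pp per phase), two phase steps plus a linear time term gave a joint test that rejected in 4.1–5.5%.

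**6. Cost in precision.** Take the phase length as the time unit. A raw difference has variance 2σ²/n.
- Common slope: the slope is estimated within all three phases, with variance σ²/(3n/12) = 4σ²/n. A step has variance (2 + 4)σ²/n, so the SE ratio is √(6/2) = 1.73. The overall change has (2 + 2² × 4)σ²/n, ratio √(18/2) = 3.0.
- Free slopes, comparing a phase mean with an earlier line extrapolated to that phase's midpoint: a one-phase slope has variance 12σ²/n. A step has (1 + 1 + 12)σ²/n, ratio √(14/2) = 2.65. The overall change has (1 + 1 + 48)σ²/n, ratio √(50/2) = 5.0.

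**7. Cost in power at 3,000 per phase, no drift.** For 40% against 43%, the raw SE is √[(0.24 + 0.2451)/3,000] = 1.27 pp.

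| Analysis | SE of step (pp) | Power, 3 pp step | Power, 6 pp overall |
|---|---|---|---|
| Raw difference | 1.27 | 66% | over 99% |
| Common slope | 1.27 × 1.73 = 2.20 | 28% | 35% |
| Free slopes | 1.27 × 2.65 = 3.36 | about 15% | 16% |

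**8. Multiplicity.** Two contrasts each tested at 0.05 would give a family-wise error of 1 − 0.95² = 9.75% if independent. These two share phase 2, so that is a guide only.

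**The case against.** The strongest reply is that the remedy can do worse than the plan.
- If adherence rises and levels off (8 pp, 4-month time constant, no effect), the free-slope overall contrast is biased by −8.1 pp, against +3.9 pp for the raw difference.
- With a ±3 pp annual cycle and no seasonal terms, its bias reaches 14.6 pp, against 0 raw.
- If the email effect builds gradually to 6 pp (2-month time constant, no drift, no guidance effect), the common-slope model returns 2.4 pp for a true overall change of 5.9 pp.

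Add the power loss, and an adjusted contrast may not settle either hypothesis. All of this stands. It argues against a complicated extrapolation model as the sole answer, and for one simple model with raw means beside it. It does not justify an omnibus test without a time term.

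It is also fair that the lack of a concurrent control belongs to the design, that the Primary outcome section does name the target quantities, and that every size above is assumed. At 0.1 pp/month and 1,000 per phase the ANOVA rejects in 7%, close to nominal.

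A reader might infer more than the text supports:
- That adherence is drifting, or that a positive result would be spurious. Nothing in the documents shows this.
- That the plan always favors the decision support. Downward drift would work against it.
- That ANOVA is invalid because the outcome is binary. With independent cases and no drift, it rejected in 4.5–4.8% of simulations.
- That the sponsor has not set switch dates. They are only absent from the text available here.

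**Conclusion.** The point holds and should be fixed before analysis. Followed as written, the plan yields a test that answers neither hypothesis and merges any drift with the phase differences. That much comes from the text and needs no assumption. The size cannot be derived from the documents: 55% false rejection at 0.25 pp/month is an illustration that depends on the assumed baseline, volume, phase length and linear drift. A time-adjusted model removes smooth drift of the form it assumes. It cannot turn a sequential uncontrolled design into a controlled one, and an event that coincides with a switch stays inseparable from the decision support.

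**What to change.** In the Statistical analysis plan:
1. Define the study groups as the three phases, and state switch dates and phase lengths. Confirm that case dates come with the extract from the data warehouse, which is named "as the data source to study the effects of the decision support on the application of prophylactic interventions for PONV".
2. Name three contrasts with 95% confidence intervals: phase 2 vs 1 (email), phase 3 vs 2 (added guidance) and phase 3 vs 1 (overall). State a multiplicity rule for the two hypotheses.
3. Estimate all three from one patient-level interrupted time series regression of exact-match adherence, with phase steps, a calendar-time term, and standard errors that allow for provider clustering and serial correlation.
4. Fix the model form once phase lengths are stated and before outcome data are examined: a common slope with phase steps, or free slopes only if phases are long enough. With free slopes, also state the time point at which contrasts are evaluated.
5. Report raw phase means and differences alongside. Give the other slope form, and the exclusion of a stated transition window after each switch, as sensitivity analyses.
6. Attach to any conclusion of added value the caveat that non-linear drift, seasonality, gradual uptake and co-occurring changes remain possible biases.

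The cost is wider intervals and lower power. With equal phases the SE is about 1.7 times the raw SE for each step and 3.0 times for the overall change (common slope), or 2.65 and 5.0 times (free slopes). The power figures above assume independent cases, so they are probably optimistic. No new patients or data sources are needed.

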Current literature on decisions support systems suggests that the design may have a great influence on what impact a CDSS has on medical decision making.[9] However, we are still only beginning to understand which CDSS design features will have the largest impact on the behavior of healthcare providers. The context of the clinical problem may be an important factor in what design for a decision support tool is the most appropriate.[5] The proposed study aims to improve the adherence to PONV guidelines by implementing multiple decision support elements with different design features.

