## Research question and hypotheses

### Research question

Does the adherence to the recommendations of a clinical decision support system for postoperative nausea and vomiting depend on the proximity of the advice to specific decisions?

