### Secondary outcomes

The occurrence of PONV within the patient's PACU admission. PONV will be defined as the administration of rescue antiemetics. The list of rescue antiemetics is similar to the list of prophylactic interventions, excluding the pre-anesthesia interventions, but complemented by the use of promethazine and compazine. Other secondary process outcome variables are: the absolute number of prophylactic interventions applied and time to discharge readiness at the PACU.

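### The only test named is a case-level ANOVA between phases, with no allowance for cases clustered within anesthesia providers, so the 5% error rate is not assured

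*Combined protocol and SAP*

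**What the plan says.** The inferential plan is two statements in the Statistical analysis plan section: a two-sided 0.05 level, and a comparison of the primary and secondary outcomes "between the study groups utilizing analysis of variances to compare the means of multiple groups".

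Other sections define what is being compared:

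- **Groups.** Study design describes a time series in three parts. "The first phase is the preintervention phase"; the email phase follows, and then email plus real-time guidance. These are the only groups defined.
- **Target of the prompt.** Under Hypotheses, the first recommendation is "sent by email to individual anesthesia providers the day before the scheduled procedure". The second appears at the start of anesthesia.
- **Outcome.** Primary outcome scores each case by an "exact match between the recommended and applied numbers of interventions", which reflects what the provider decided to give. One secondary outcome, "the absolute number of prophylactic interventions applied", is a provider decision in the same way.
- **Purpose.** Background says little is yet known about "which CDSS design features will have the largest impact on the behavior of healthcare providers". The Research question asks whether adherence may "depend on the proximity of the advice to specific decisions". Neither limits the question to the staff who happened to be working.
- **Data.** Data collection names the perioperative data warehouse "as the data source to study the effects of the decision support on the application of prophylactic interventions" and lists no provider field.

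No section mentions a provider term, a mixed model, GEE or a clustered variance.

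**The concern.** Study population admits every eligible case in the study period, so one provider will plausibly contribute many cases. An ordinary ANOVA treats those cases as independent.

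Both hypotheses are contrasts between phases. If providers react unevenly to the email or the real-time prompt, or if the mix of staff or their caseloads shifts between phases, the naive standard error can be too small. A chance shift among a few high-volume providers could then be declared an effect of the decision support system. Uneven reaction is foreseeable, because the prompts are meant to change provider behavior.

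The opposite case is also possible. If the same providers work in all phases with the same caseloads and the same behavior, the naive test is about right. The document does not let a reader tell which case applies.

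**Working it through.** **Inputs.** The document supplies the 0.05 two-sided level, three phases and a binary outcome. It states no sample size, power, effect size or baseline adherence, so there is no planned figure to reproduce. Everything else is assumed: 40% adherence, 60–150 providers, 20–50 cases per provider per phase, and provider intraclass correlation (ICC) 0.01–0.10.

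**What cancels and what does not.** Let m be the cases per provider per phase. Let ρb be the share of outcome variance from stable provider differences, and ρi the share from provider-by-phase variation. With the same providers and equal caseloads, the true variance of a phase contrast divided by the variance that ANOVA assumes is

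R = 1 − ρb + (m − 1)ρi.

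Stable differences make the test slightly conservative. Provider-by-phase variation inflates R in proportion to m. With many cases, the level of the three-phase F test is about P(χ²₂ > 5.99/R) = exp(−5.99/(2R)). If staff differ completely between phases, R = 1 + (m − 1)ρb.

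| Setting | R | Formula | Simulated ANOVA (4,000 runs each) |
|---|---|---|---|
| Stable, ρb 0.10 | 0.90 | 3.6% | 3.0–3.7% |
| Stable, ρb 0.05 | 0.95 | 4.3% | 4.0–4.4% |
| m 50, ρb 0.05, ρi 0.01 | 1 − 0.05 + 0.49 = 1.44 | 12.5% | 11.9–12.8% |
| m 50, ρb 0.05, ρi 0.02 | 1 − 0.05 + 0.98 = 1.93 | 21.2% | 20.4–21.1% |
| m 50, ρb 0.05, all staff different | 1 + 49 × 0.05 = 3.45 | 42.0% | 42.0–42.6% |

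The same simulations gave 7–28% when caseloads varied between phases (coefficient of variation about 0.5), and 9–45% when half the staff changed at each phase.

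**Pairwise contrasts, which the hypotheses need.** On the logit scale, a provider-by-phase SD of s corresponds to ρi ≈ p(1 − p)s² = 0.24s² at 40% adherence. Ignoring the small ρb term:

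- s = 0.2, m = 30, equal caseloads: ρi = 0.0096. The variance ratio is 1 + 29 × 0.0096 = 1.28, the SE factor is 1.13, and the level is 2[1 − Φ(1.96/1.13)] ≈ 8.3%.
- s = 0.4, m = 50, caseloads following a gamma distribution with shape 2 (squared coefficient of variation 0.5, so effective m = 75): ρi = 0.0384. The variance ratio is 1 + 74 × 0.0384 = 3.84, the SE factor is 1.96, and the level is about 31.7%.

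A three-phase null simulation covered 96 scenarios of 3,000 runs with uneven caseloads and 24 of 2,000 runs with equal caseloads. Monte Carlo error was about 0.8–1.0 points at 5%. Levels of the naive pairwise test were:

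| Condition | Naive pairwise test |
|---|---|
| Stable providers | 4.3–5.6% |
| Provider-by-phase SD 0.1 | 5.4–7.6% |
| SD 0.2–0.4 (SE factor 1.12–1.92) | 7.5–31% |
| 20% random turnover only, ICC 0.01 | 4.6–6.9% |
| 20% random turnover only, ICC 0.10 | 10–18% |
| SD 0.3 plus 20% turnover | 12–30% |

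The provider-clustered pairwise test gave 4.0–6.6% throughout. A separate 2,000-run check of the mildest SD 0.2 setting (60 providers, 30 cases, equal caseloads) gave 6.5% naive and 4.2% clustered, so the low end is better read as about 7%.

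**Omnibus test and varying caseload.** At SD 0.2–0.4 the ANOVA F test rejected 9–45% of the time and a provider-clustered Wald test 4.3–6.8%. A further null simulation with assumed inputs gave the following for ANOVA F: about 5% with stable providers, 16–29% at SD 0.2–0.3, 6–28% with 20% turnover, and 13–27% with caseload varying between phases. In the same runs the clustered pairwise test gave 4.6–6.3% and the clustered omnibus test 4.6–7.5%.

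**The case against.** The strongest reply concerns what is being estimated. The data come from one institution's warehouse, and all eligible cases in the period are taken. If the target is the providers actually studied, a realized shift in their average behavior is a real change, not a false positive. Moreover, if the prompts do nothing, no one reacts to them, and only unrelated drift or staffing change remains. The larger illustrations also need individual providers to move a good deal around a zero mean. At 40% adherence, SD 0.2 per phase implies a between-phase SD of 0.24 × 0.2 × √2 ≈ 7 percentage points, and SD 0.4 about 14. Nothing in the document supports those values.

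Part of this stands. The sizes are illustrations and say nothing specific about this trial. A finite-provider target could be defended, but the plan does not state one, and its background and research question are posed without that limit. Staffing and caseload changes also inflate the error without any reaction to the prompts.

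A second reply is that calendar trend is the larger threat in an uncontrolled sequence of phases. That is fair. With no system effect, the clustered test still rejects 24–70% of the time under a 2-point secular drift. It rejects 16–43% of the time if 20% of providers are replaced by staff 0.5 logits more adherent. Clustering is a separate omission, and correcting it does not remove those biases.

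**Conclusion.** The concern holds in conditional form. The planned ANOVA keeps its 5% level if providers, their caseloads and their responses are the same in every phase. It does not if any of these differs, and the document rules out none of them.

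The error rate ranges from no inflation to several times nominal, depending wholly on assumed provider numbers, caseloads, ICC and turnover. With low ICC and modest turnover the excess is negligible. With ICC 0.10 or clear provider-by-phase variation it is not. The omission touches both hypotheses and is cheap to repair, so it should be fixed. Confidence is medium, because the provider data that would settle the size are absent.

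**What to change.** State that each phase contrast (email versus preintervention, email plus real-time versus email, and overall) will be estimated in one of two ways:

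- regression or GEE with provider-clustered robust standard errors; or
- a mixed model with provider and provider-by-phase effects.

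The plan should also:

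- name one recorded provider role as the cluster, and confirm that the warehouse holds it for all three phases, since sending emails later does not show that provider identity was recorded preintervention;
- report the number of providers, cases per provider and provider overlap between phases;
- add a sensitivity analysis restricted to providers present in both phases of a contrast;
- treat the number of prophylactic interventions in the same way;
- say so explicitly if inference is meant only for the providers studied.

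The cost is SAP wording, one data check and usually wider confidence intervals. With stable providers and a true rise of about 4 points, simulated power is 70.0% naive versus 69.2% clustered (60 providers, 30 cases each per phase), and 87.9% versus 87.1% with 50 cases. The cost when providers do vary was not simulated. Clustering on one role may leave correlation within the wider anesthesia team unmodelled. Secular trend and systematic staff change need separate handling.

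### The only stated inference, an ANOVA across three consecutive phases, decides neither hypothesis by itself; the two named effects have no stated interval or testing rule, and there is no term for calendar time.

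*Combined protocol and SAP*

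**What the plan says.** - Hypotheses: "The research question will be addressed in this study by testing the following hypotheses". The first is that a recommendation "sent by email to individual anesthesia providers the day before the scheduled procedure increases the adherence to PONV guidelines". The second is that a recommendation "presented at the start of anesthesia increases the adherence to PONV guidelines (and has an added value to the automated email recommendation").
- Study design: "The time series consists of three phases", namely before any decision support, email only, and then real-time guidance, which "is being displayed along with the email intervention". Because the email continues into the third phase, the added value of real-time guidance is the comparison of phase 3 with phase 2.
- Primary outcome: a yes/no result per patient (exact match or not). "For the primary analysis the overall change in adherence as well as the added values of the different decision support elements" are to be quantified.
- Statistical analysis plan: "A two-sided alpha of 0.05 will be considered to be statistically significant". Outcomes are compared between study groups "utilizing analysis of variances to compare the means of multiple groups". Discrete variables are described as numbers with percentages.

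No section names a contrast, an effect measure, a confidence interval, an order of testing, a multiplicity rule, a regression model or a time term.

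**The concern.** The target effects are fixed in words, but the only test described is aimed at a different question: whether the three phase means are all equal. A significant result would leave open which step changed and in which direction. The contrasts, their intervals and the testing rule would then be chosen when the data are already in hand.

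The second gap concerns time. The phases run one after another, so calendar time and intervention order are aligned. If adherence was already moving for other reasons, phase means differ even when neither decision-support element does anything, and an ANOVA without a time term counts that difference as signal. At stake is whether the study can say that the email works, whether real-time guidance adds to it, and whether either change exceeds the trend already under way.

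**Working it through.** The documents give no sample size, phase length, base rate or target effect, so there is no figure of the plan's own to reproduce.

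**Inputs from the documents:** three consecutive phases; a binary primary outcome; two-sided alpha 0.05; ANOVA across groups. **Assumed:** 40% adherence in phase 1; equal phases of 2,990 patients over 26 weeks or 1,000 over 25 weeks; independent patients; linear drift.

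**1. What F tests.** Write d1 = phase 2 minus phase 1 and d2 = phase 3 minus phase 2. With n per phase and average binomial variance s², the noncentrality of F is

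λ = n × (2/3)(d1² + d1·d2 + d2²) / s².

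Swapping d1 and d2, or reversing both signs, leaves the bracket unchanged. At n = 1,000:
- Only email works (40/50/50%): λ = 1,000 × 0.00667 / 0.2467 = 27.0.
- Only real-time guidance works (40/40/50%): λ = 1,000 × 0.00667 / 0.2433 = 27.4.
- Adherence falls (50/40/40%): λ = 27.4.

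F rejects in 99.8% of trials in all three. In simulation of the second case, F was significant without a significant rise from phase 1 to phase 2 in 97% of runs.

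**2. Error rate of the two contrasts when nothing works.** They share phase 2 with opposite signs, so their correlation is −(s²/n)/(2s²/n) = −0.5. Then P(|Z1| > 1.96 or |Z2| > 1.96) = 9.1%; if they were independent it would be 1 − 0.95² = 9.75%. Simulation over four sets of equal and unequal phase sizes gave:
- no rule: 8.6 to 9.3%
- only after a significant F: 3.9 to 4.2%
- Holm on the two: 4.4 to 4.7%

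**3. Background trend, no intervention effect.** With equal steps d between phases, λ = 2n·d²/s². The step is the monthly drift times 6 months (26 weeks) or 25 × 12/52 = 5.77 months (25 weeks).

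| Per phase | Drift, pp/month | Step, pp | λ | F rejects |
|---|---|---|---|---|
| 2,990 | 0.25 | 1.50 | 5,980 × 0.0150² / 0.2426 = 5.5 | 55% |
| 2,990 | 0.5 | 3.00 | 5,980 × 0.0300² / 0.2445 = 22.0 | 99% |
| 1,000 | 0.25 | 1.44 | 2,000 × 0.0144² / 0.2425 = 1.7 | 20% |
| 1,000 | 0.5 | 2.88 | 2,000 × 0.0288² / 0.2444 = 6.8 | 64% |

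In simulation, level changes from a model with a linear time term rejected in about 5% each; that model is correctly specified here because the simulated drift is linear. Naming contrasts does not cure this part: F-gated raw contrasts gave at least one false attribution in 39% and 95% of runs at 2,990 per phase, and 14% and 46% at 1,000.

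The 40% base does not flatter the concern. The variance p(1−p) is 0.24 there, near its maximum of 0.25; at 20% or 80% it is 0.16, which makes λ about 1.5 times as large.

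**4. Price of the time term.** Let each phase have length L.
- The raw contrast has variance 2s²/n.
- A common slope has variance s²/(3n·L²/12) = 4s²/(nL²). The level change (raw contrast minus slope × L) therefore has variance 2s²/n + 4s²/n = 6s²/n, and its standard error is √3 = 1.73 times the raw one.
- With phase-specific slopes the variance is 8s²/n, a factor of 2.

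At 2,990 per phase the raw 95% half-width is 1.96 × √(2 × 0.24/2,990) = 2.5 pp, so the adjusted ones are 4.3 and 5.0 pp. Simulated power for a 5 pp effect is 98% raw, 62% with a common slope and 50% with phase-specific slopes; at 1,000 per phase it is 61%, 25% and 20%. The formulas agree within about 1 pp.

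**The case against.** The strongest reply is that the SAP section should not be read alone. The Primary outcome section promises to quantify the added values, and the SAP reports discrete variables as percentages. A reader following both would tabulate adherence by phase and take differences. That stands. A reader might infer that the plan never estimates the effects, or can say nothing about the email, and the documents do not support that. What is missing is the stated inference for those differences.

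Second, contrasts commonly follow a significant ANOVA, and with three groups that sequence controls the error. This also stands, so 9% must not be read as the plan's error rate. It is the result under one of two readings that the text leaves open.

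Third, the drift is hypothetical. Nothing in the documents shows that adherence was changing, and the effect depends on drift and phase size, as the range from 20% to 99% shows. A reader might infer that no result of this study could be interpreted; that goes too far. What holds without any drift figure is that the raw comparison cannot tell a trend from an effect.

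Fourth, low power of individual contrasts at modest sizes is a matter of sample size and is not counted here as harm from the missing specification.

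Finally, reading the study groups as the three phases is an inference, but the Study design section defines no other groups.

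**Conclusion.** The point holds as a gap in the analysis plan that should be fixed. That the three-group F test decides neither the first hypothesis nor the added-value part of the second follows from the text and needs no assumption. The consequence for error control is a choice between about 9% and about 4% that the plan leaves unmade.

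The missing time term goes beyond missing detail, because the stated method gives a wrong answer under a trend: false rejection in 20 to 99% of trials across the assumed drifts and sizes, against about 5% for the time-adjusted level change. Those rates rest on assumed phase sizes, phase lengths, base adherence, linear drift and independent patients. They measure sensitivity and are not evidence that drift occurred. Provider clustering or autocorrelation was not modelled and would usually widen intervals.

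**What to change.** In the Statistical analysis plan section:

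1. Name two primary contrasts, phase 2 minus phase 1 and phase 3 minus phase 2. Report each as a risk difference with a 95% confidence interval. State one testing rule: either test them at two-sided 0.05 only after a significant three-group F, or apply Holm to the two. Report phase 3 minus phase 1 as an estimate.
2. Pre-specify a segmented model with a calendar-time slope and level changes at the two start dates, with phase-specific slopes as a sensitivity check. Report its level changes and intervals beside the raw contrasts. State that a raw contrast which the time-adjusted estimate does not support will be described as a difference between phases and not as an intervention effect. The sponsor should define support before looking at outcomes; the documents offer no basis for a numerical threshold.

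**Cost.** SAP wording only, with no new data. The testing rule costs some power: when only the email works and adds 5 pp, the email contrast at 1,000 per phase has about 62% power with no rule, 55% with the F gate and 51% with Holm; at 2,990 per phase the gate gives 97% and Holm 95%. The segmented model costs more, as the last step of the working shows. It also assumes a linear trend, and a common slope is biased if the trend changes between phases. The SAP should disclose these limits.
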